3.1 Background

Vitiligo is an acquired, non-contagious skin disorder characterised by depigmented patches of skin that may appear in a localised or very generalised distribution, and affecting 0.5-2.0% of the global population.(1) The exact cause of the loss of functioning melanocytes in vitiligo remains unknown, but is likely to be resulted from the complex interplay of genetics, oxidative stress, and autoimmunity.(2)

Although vitiligo is typically asymptomatic, recent Pfizer-funded research has demonstrated the condition substantially affects psychological wellbeing.(3) This previous study showed that people with vitiligo have a considerable excess mental health burden when compared with people without vitiligo. It also showed that, in people with vitiligo, mental health comorbidity is associated with higher levels of healthcare utilisation, time off work, and unemployment.(3) This increased burden could be due to the unpredictable prognosis, the current lack of cure, the perception and emotional burden associated with the visibility of vitiligo, or a combination of these factors.

There is substantial scope to extend the initial analysis, with a comprehensive assessment of sociodemographic disparities in healthcare utilisation and in the burden of mental health comorbidity in people with vitiligo. Whilst the previous Pfizer-funded study demonstrated a difference by ethnicity in the mental health impacts of vitiligo (with vitiligo associated with a greater mental health burden in people of non-white ethnicity), the study was not designed to assess this as a primary outcome. Further analysis is required to fully understand these potential relationships as well as provide critical information on whether there is a socio-economic (SES) gradient in the mental health impacts of vitiligo. The previous study did not assess other potential disparities in management, such as healthcare utilisation of primary care encounters or dermatology services.

There is also substantial scope to expand on the previous study to provide, for the first time, a greater understanding of the total burden of vitiligo across the population, including reporting lifetime risk estimates for vitiligo, across sociodemographic groups. It is likely that substantial disease burden differences exist across these groups.

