7.3 Matching Process

For objectives 2-5, controls for each vitiligo case will be identified from the pool of people without a vitiligo diagnosis registered in the OPCRCD database at the time of vitiligo diagnosis for the case. Vitiligo cases will be eligible as controls up until the date of their vitiligo diagnosis (at which date their follow-up will be censored if selected as a control).

Each case will be assigned an index date at the time of their vitiligo diagnosis. Corresponding controls assigned to each case will have the same index date.

Each individual with vitiligo will be matched at their index date with up to four unaffected controls. Controls cannot be diagnosed with vitiligo at the date of matching and will require at least one year of follow-up time to minimise the risk of a non-recorded existing diagnosis of vitiligo. Time-updated exact matching will be performed by age, sex, ethnicity and deprivation, selected from the pool of eligible people registered in the same GP practice.

If required, a combination of time-dependent propensity score matching and exact matching will be performed to create a baseline matched dataset.

The matching process is subject to change depending on the feasibility of the mentioned matching process during the initial exploration of the data. The produced baseline matched dataset will be used for all analyses for objective 2-5.

8. Statistical Analysis

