8.1 Statistical Principles

Mean, standard deviation (sd) and any other statistical measures, will be reported to one decimal place. Continuous data will be summarised in the form of means, sd, median, interquartile range (IQR) and range as appropriate. Categorical data will be summarised using the frequencies and proportions. Chi-squared and t-tests will be performed to compare the frequency of dichotomous variables and the values of continuous variables where relevant. 95% CIs will be reported for main effect sizes. Statistical significance will be assessed using $p < 0.05$. Actual p-values will be reported except for p-values less than 3 decimal places which will be reported as “ < 0.001 ”. P-values > 0.1 will be reported to one decimal place, p-values between 0.01 and 0.1 will be reported to 2 decimal places, and p-values between 0.001 and 0.01 will be reported to three decimal places.

The assessment of any associations with baseline characteristics and the outcomes of interest (objectives 2-5) will be assessed using logistic regression (prevalent and incident outcomes), Cox proportional hazards (time to event outcomes) and Poisson regression (repeated event outcomes) models. Three different adjustment sets will be used for each endpoint analysis. These include: an unadjusted model, a sex and age adjusted model, and a multivariable model with an adjustment set of: age, sex, BMI, smoking status, alcohol use, and common comorbidities: type 2 diabetes, hypertension, atrial fibrillation, angina, acute myocardial infarction, stroke, heart failure, chronic liver disease, dementia, rheumatoid arthritis, asthma, chronic obstructive pulmonary disease, chronic kidney disease stages 3-5, malignancy and inflammatory bowel disease.

Assumptions of statistical approaches will be assessed, and transformations used if necessary.

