8.3 Secondary Endpoint Analysis

Objective 2

Anxiety and depression outcomes will be captured if occurring prior to, or within two years of, an individuals' study index date. Binary outcome logistic regression model outputs will be used to compare the burden of anxiety and depression in vitiligo cases compared to matched controls. Furthermore, additional analyses for new onset anxiety and depression outcomes will be conducted, excluding people with a previous record of the respective mental health condition. Anxiety and depression outcomes will be defined by the first occurrence of a relevant code in the primary care record up to two years post index-date. Cox proportional hazards regression will be used to estimate the excess risk of anxiety and depression outcomes in vitiligo cases versus controls. Results will be described as hazard ratios.

Objective 3

Parasuicide/suicide attempts will be defined by the first occurrence of a relevant code in the primary care record up to two years post index-date. People with a previous record of parasuicide/suicide attempt will be excluded from the calculations. Cox proportional hazards regression will be used to estimate the excess risk of parasuicide/suicide attempts in vitiligo cases versus matched controls. Results will be described as hazard ratios.

Adjustment disorder and sleep disturbance will be defined by the first occurrence of a relevant code in the primary care record up to two years post index-date. People with a previous record of the adjustment disorder will be excluded from the from the adjustment disorder endpoint analysis. Cox proportional hazards regression will be used to estimate the excess risk of the relevant condition in vitiligo cases versus matched controls. Results will be described as hazard ratios.

Objective 4

Dermatology referral and mental health referral or reviews will be defined by the first occurrence of a relevant code in the primary care record up to two years post index date. Cox proportional hazards regression will be used to estimate the excess risk of these outcomes in vitiligo cases versus matched controls.

For primary care encounters reviews, defined as a rate of encounters within two years after the index date, will be compared using generalised linear models with time-at-risk as an offset. Results will be described as incidence rate ratios.

Objective 5

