402368008		Ichthyosiform sarcoidosis (disorder)
402373002		Hypomelanotic sarcoidosis (disorder)
9529007		Sarcoidosis, erythrodermic type (disorder)
72470008		Sarcoidosis, lupus pernio type (disorder)
402372007		Subcutaneous nodular sarcoidosis (disorder)
238675007		Sarcoidosis-induced erythema nodosum (disorder)
238676008		Lofgrens syndrome (disorder)
31541009		Lupus pernio of Besnier
231799005		Sarcoid skin of eyelid (disorder)

Appendix 2

Potential differential diagnoses for vitiligo which will be used as exclusion criteria if they appear as diagnoses in the medical record within six months of the initial diagnosis of vitiligo (six months before or after the vitiligo diagnosis). *As these conditions are extremely uncommon in the UK they will not be used in the exclusion process. Codes for these conditions are listed in Appendix 1.

Condition group	Conditions/causes included
Congenital and genetic hypomelanoses	Piebaldism Tuberous sclerosis Hypomelanosis of Ito Waardenburg syndrome Hermanski-Pudlak syndrome Griscelli syndrome Menkes syndrome
Post-inflammatory hypomelanoses	Post-inflammatory leukoderma including after Atopic eczema or Psoriasis Lichen planus Pityriasis alba Lichen sclerosus
Post traumatic leukoderma	Post traumatic leukoderma
Para-malignant hypomelanoses	Cutaneous T-cell lymphoma (mycosis fungoides) Melanoma associated depigmentation
Occupational/drug induced hypomelanoses	Occupational vitiligo Other induced hypomelanoses
Para-infectious hypopigmentation	Pityriasis versicolor (or tinea versicolor) Leprosy* Leishmaniasis*
Others	Melasma Morphoea Idiopathic guttate hypomelanosis Xeroderma pigmentosum Progressive macular hypomelanosis Nevus depigmentosus Cutaneous sarcoidosis

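### The multivariable set in Section 8.1 omits thyroid disease, type 1 diabetes, atopic eczema and psoriasis, so the case-control ratios may carry residual confounding

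*Combined protocol and SAP*

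**What the plan says.** Section 8.1 plans three levels of adjustment for Objectives 2-5: none, age and sex, and "a multivariable model with an adjustment set of: age, sex, BMI, smoking status, alcohol use" plus a comorbidity list. The list opens with "common comorbidities: type 2 diabetes, hypertension, atrial fibrillation, angina, acute myocardial infarction, stroke, heart failure, chronic liver disease, dementia, rheumatoid arthritis, asthma" and closes with "chronic obstructive pulmonary disease, chronic kidney disease stages 3-5, malignancy and inflammatory bowel disease". That is eleven conditions plus four, so 15.

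Section 7.3 does not match on comorbidity: "Time-updated exact matching will be performed by age, sex, ethnicity and deprivation", within the same GP practice. A fallback is allowed ("If required, a combination of time-dependent propensity score matching and exact matching will be performed"), but its covariates are not listed.

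Section 3.1 describes the loss of melanocytes in vitiligo as "likely to be resulted from the complex interplay of genetics, oxidative stress, and autoimmunity". For Objective 4, Section 8.3 states: "Dermatology referral and mental health referral or reviews will be defined by the first occurrence of a relevant code", counted over two years from the index date. Primary care encounters are the other utilisation outcome.

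Among the differential diagnoses to be excluded, Appendix 2 lists "Post-inflammatory leukoderma including after Atopic eczema or Psoriasis". Appendix 1 holds no code for eczema or psoriasis themselves. The three sensitivity analyses in Section 8.4 concern non-attending controls, a four-year outcome period and missing ethnicity. None adds a covariate.

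**The concern.** The 15 conditions look like a general chronic-disease list, not one built around vitiligo. The plan calls autoimmunity a likely cause and already adjusts for rheumatoid arthritis and inflammatory bowel disease, so it accepts in principle that immune-mediated comorbidity should be adjusted for. It gives no reason for stopping short of thyroid disease, or for listing type 2 but not type 1 diabetes. Either omitted condition could plausibly affect mood, sleep and consultation rates.

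The argument is strongest for skin disease. Eczema or psoriasis is itself a reason to see the GP and to be referred to dermatology, and it also brings the skin to a clinician's attention, which could make a vitiligo code more likely. A condition that can raise both the chance of being a case and the chance of the outcome is a potential confounder. Nothing in the design removes it.

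At stake is how far an adjusted hazard, odds or rate ratio can be read as belonging to vitiligo. Section 9 says disparities will be interpreted on the assumption that the outcomes are related to it.

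**Working it through.** **1. Coverage.** Adjustment, matching, exclusion and sensitivity analysis were each checked for the four conditions. None names thyroid disease or type 1 diabetes. Eczema and psoriasis appear only as antecedents of a leukoderma in Appendix 2, so a person with either condition and no such leukoderma code stays in the study.

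**2. Yardstick from Section 6.** The stated detectable differences convert to ratios:
- anxiety: (15 + 1.11)/15 = 1.074
- depression: (10 + 1.12)/10 = 1.112

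The differences themselves do not reproduce. The Kelsey formula, n1 = (z_a + z_b)² p̄(1 − p̄)(r + 1)/(r d²), solved for d at n1 = 8,000, two-sided 5%, 80% power and r = 4, gives 1.26 points for anxiety and 1.06 for depression. Section 6 restates neither the matching ratio nor the sidedness. That is a separate matter. With the recomputed values the ratios are 16.26/15 = 1.084 and 11.06/10 = 1.106, so the yardstick hardly moves.

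**3. Bias factor.** For an omitted binary condition with prevalence p1 in cases and p0 in controls, and risk ratio RR for the outcome,

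B = [1 + p1(RR − 1)] / [1 + p0(RR − 1)].

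If p1 = p0, then B = 1 and there is no confounding. The documents supply none of these inputs. **All prevalences and risk ratios below are assumptions**, for depression or anxiety as the outcome. Multiplying the two factors treats the conditions as independent with multiplicative effects.

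| Case | Thyroid (cases v controls; RR) | B | Eczema or psoriasis | B | Product |
|---|---|---|---|---|---|
| Low | 8% v 4.5%; 1.3 | 1.0240/1.0135 = 1.010 | 15% v 12%; 1.2 | 1.030/1.024 = 1.006 | 1.016 |
| Midpoint | 11% v 4.5%; 1.5 | 1.0550/1.0225 = 1.032 | 17.5% v 12%; 1.35 | 1.06125/1.0420 = 1.018 | 1.051 |
| High | 14% v 4.5%; 1.7 | 1.0980/1.0315 = 1.064 | 20% v 12%; 1.5 | 1.10/1.06 = 1.038 | 1.105 |

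In percentage points, baseline × (B − 1):
- anxiety at 15%: 0.24, 0.76 and 1.57, against the stated 1.11
- depression at 10%: 0.16, 0.51 and 1.05, against the stated 1.12

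Only the high case for anxiety exceeds its stated detectable difference. Type 1 diabetes is not included in these figures.

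**4. Wider inputs, one condition at a time (assumed).** 5% v 3% with RR 1.5 gives 1.025/1.015 = 1.010. 10% v 5% with RR 2 gives 1.10/1.05 = 1.048. 30% v 15% with RR 3 gives 1.60/1.30 = 1.231.

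**5. Dermatology referral (assumed).** Keep the eczema or psoriasis prevalences above and let RR for referral be 2 to 3. The factor runs from 1.15/1.12 = 1.03 to 1.40/1.24 = 1.13. This is an illustration only, since the documents give no referral rates.

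**6. Disparities (assumed).** Take thyroid disease at 6% v 3% in men and 12% v 6% in women, RR 1.4. Then B = 1.024/1.012 = 1.012 in men and 1.048/1.024 = 1.023 in women. The spurious ratio between the sexes is 1.023/1.012 = 1.011, about 1.1%.

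**The case against.** The strongest reply is that the premise is not in the documents. No section says that any of the four conditions is commoner in people with vitiligo. Section 3.1 says only that autoimmunity probably contributes, and Appendix 2 treats eczema and psoriasis as antecedents of a different diagnosis. This stands: confounding is possible, not shown.

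The plan also covers part of the ground. Rheumatoid arthritis and inflammatory bowel disease are in the set. Lichen planus, lichen sclerosus, pityriasis alba, morphoea, cutaneous sarcoidosis and others are excluded when coded within six months of the vitiligo diagnosis. Because that window is anchored to the vitiligo diagnosis, it removes skin disease mainly from cases, which would push the referral ratio the other way. The net direction for referral is therefore not established. The attending-controls analysis in Section 8.4 partly addresses detection through contact with the practice, but it is not specific to skin consultations. None of this reaches the four conditions.

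Third, the Section 6 figures are detectable differences, not expected effects, and Section 3.1 reports a considerable mental health excess in the earlier study. Against a large true effect, a factor of 1.05 matters less. That is fair.

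Lastly, the objectives are descriptive, and Section 9 rules out causal interpretation for utilisation and work outcomes. It gives no such caveat for mental health or sleep, and Section 8.3 still sets out to estimate excess risk in cases.

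**Conclusion.** The gap is real and the plan does not address it: four plausible confounders are outside the multivariable set and outside every other design step. The supportable conclusion is that the case-control ratios for mental health, sleep, primary care visits and especially dermatology referral **may** carry residual confounding of unknown size. For depression or anxiety the assumed inputs give a factor of about 1.02 to 1.10. That could be negligible or could approach the smallest effect the study claims to detect. It rests wholly on assumed prevalences and risk ratios, on independence of the conditions, and on applying a risk-ratio formula to hazard and odds ratios.

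A reader might infer two stronger things. One is that effects of these conditions **are** being credited to vitiligo. The documents contain no co-occurrence data, so neither the existence nor the direction of bias is established. The other is that the reported sociodemographic disparities are distorted by a similar amount. A disparity is distorted only so far as the bias factor differs between subgroups. Nothing in the documents quantifies that, and the illustration suggests a smaller effect. This is a low-cost improvement, not a flaw that invalidates the analysis.

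**What to change.** In Section 8.1, add thyroid disease, type 1 diabetes, atopic eczema and psoriasis to the multivariable set for Objectives 2-5, each defined as a code before the index date. At minimum, prespecify this as a sensitivity model in Section 8.4. Tabulate the four conditions by case status and by sociodemographic subgroup, so that readers can see whether they differ at all. If they do not, the concern falls away.

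State one limit: the Objective 2 burden model counts anxiety and depression recorded before the index date, so a pre-index covariate may follow the outcome there. The 15 conditions already listed share that limit. The new-onset Cox analyses exclude people with a prior record of the outcome and are cleaner in this respect.

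The cost is four code lists and four binary terms, with about 8,000 cases expected and diagnoses already held in the primary care record (Section 5.4). The models become slightly larger.

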8.2 Primary Endpoint Analysis

Objective 1

Lifetime risk of vitiligo will be calculated for the population as a whole and by sex, ethnicity, and SES. Ethnicity will be grouped using the standardised definitions of major UK ethnic groups: white, black, Asian, mixed, and other.(7) SES will be defined using the national deprivation measure; IMD.(12)

Lifetime risk will be calculated using methods to estimate cumulative lifetime risk recently published in the Lancet,(13, 14) accounting for the competing risk of death. Key outputs will be lifetime risk plots, presenting the cumulative risk of vitiligo against age for the whole population and for sociodemographic subgroups. At a particular age, the cumulative risk estimate can be interpreted as the lifetime risk of vitiligo up until and including the year of age in question. Age of 80 is considered to be the approximate

lifetime expectancy in the UK,(15) and will be the point of comparison at which the lifetime risk of vitiligo will be compared across sociodemographic subgroups.

8.3 Secondary Endpoint Analysis

Objective 2

Anxiety and depression outcomes will be captured if occurring prior to, or within two years of, an individuals' study index date. Binary outcome logistic regression model outputs will be used to compare the burden of anxiety and depression in vitiligo cases compared to matched controls. Furthermore, additional analyses for new onset anxiety and depression outcomes will be conducted, excluding people with a previous record of the respective mental health condition. Anxiety and depression outcomes will be defined by the first occurrence of a relevant code in the primary care record up to two years post index-date. Cox proportional hazards regression will be used to estimate the excess risk of anxiety and depression outcomes in vitiligo cases versus controls. Results will be described as hazard ratios.

Objective 3

Parasuicide/suicide attempts will be defined by the first occurrence of a relevant code in the primary care record up to two years post index-date. People with a previous record of parasuicide/suicide attempt will be excluded from the calculations. Cox proportional hazards regression will be used to estimate the excess risk of parasuicide/suicide attempts in vitiligo cases versus matched controls. Results will be described as hazard ratios.

Adjustment disorder and sleep disturbance will be defined by the first occurrence of a relevant code in the primary care record up to two years post index-date. People with a previous record of the adjustment disorder will be excluded from the from the adjustment disorder endpoint analysis. Cox proportional hazards regression will be used to estimate the excess risk of the relevant condition in vitiligo cases versus matched controls. Results will be described as hazard ratios.

Objective 4

Dermatology referral and mental health referral or reviews will be defined by the first occurrence of a relevant code in the primary care record up to two years post index date. Cox proportional hazards regression will be used to estimate the excess risk of these outcomes in vitiligo cases versus matched controls.

For primary care encounters reviews, defined as a rate of encounters within two years after the index date, will be compared using generalised linear models with time-at-risk as an offset. Results will be described as incidence rate ratios.

Objective 5

Only cases and matched controls aged 18-65 will be considered for this analysis. Work impact outcomes (unemployment and time off work for illness) will be defined by the first occurrence of a relevant code in primary care record up to two years post index date. Cox proportional hazards regression will be used to estimate the excess risk of these outcomes in vitiligo cases versus matched controls. Results will be described as hazard ratios.

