3.2 Purpose of Analysis

This study will provide the first estimate of the cumulative lifetime risk of vitiligo in the population overall, and by important sociodemographic groups, including age, sex, ethnicity and SES, which will provide key data to show the relative burden of vitiligo across the aforementioned groups. These approaches allow creation of cumulative lifetime risk plots which provide an excellent and accessible way to display the relative disease burden across groups.

This study will provide a detailed assessment of any sociodemographic disparities in comorbidities and social impact that occurs in people with vitiligo. This will include any differences in mental health impact of vitiligo by sociodemographic. It will also include a description of any sociodemographic disparities in time off work (“sick leave”) or unemployment in people with vitiligo.

This study will also provide a detailed assessment of any sociodemographic disparities in healthcare utilisation in people with vitiligo with comparison across sociodemographic. This will include analysis of utilisation of primary care services, mental health referrals as well as referrals to secondary care (dermatology).

4. Study objectives and endpoints

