4.1 Study Objectives

The overall purpose of the study is to provide an estimate of the lifetime risk of vitiligo in the population overall and by important sociodemographic groups. Moreover, to do a subgroup analysis in the vitiligo population to identify health-related disparities across people in different sex, age, deprivation and ethnicity.

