4.3 Secondary Objectives

4.3.1 Objective 2

Describe any disparities in the burden of mental health outcomes, including depression and anxiety in people with vitiligo across sociodemographic subgroups.

4.3.2 Objective 3

Describe any disparities in the association of vitiligo with parasuicide/suicide attempts, adjustment disorder and sleep disturbances associated with vitiligo across sociodemographic subgroups.

4.3.3 Objective 4

Describe any disparities in vitiligo-associated healthcare utilisation across sociodemographic subgroups.

4.3.4 Objective 5

Describe any disparities in vitiligo-associated work impact (time off work for illness and unemployment) across sociodemographic subgroups.

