All adults and adolescents (aged 13+ for disparity objectives 2-5 inclusive) contributing to OPCRd during the study period (January 1, 2004 and December 31, 2020 inclusive). People who have opted out of record data sharing will not be included (approximately 1.8% of the adult population) and have not been uploaded to the OPCRd database.

Cumulative lifetime risk of vitiligo will be estimated (using the method described in the statistical methods below) using cases of incident vitiligo occurring during the observational study period (January 1, 2004 and December 31, 2020 inclusive). A matched-cohort design will be used for incident (and prevalent) vitiligo related mental health conditions, healthcare utilisation and work impacts. For all analyses, the overall result including both adults (aged 18+) and children (aged 13-17) will be published, with stratification by age, sex, deprivation and ethnicity.

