5.2 Total disease burden; cumulative lifetime risk

A cross sectional design (incidence) will be used to assess the total disease burden of vitiligo, stratified by sociodemographic groups.

5.3 Disparities in the impact of vitiligo on mental health, healthcare utilisation and work impact

A matched-cohort design will be used for incident (and prevalent) vitiligo related: Mental health conditions; work impact; healthcare utilisation.

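### Objectives 2-5 ask for disparities between sociodemographic subgroups, but the analysis section specifies only vitiligo-versus-control contrasts and leaves the contrast between strata undefined

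*Combined protocol and SAP*

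**What the plan says.** The secondary objectives (Section 4.3) are worded as between-group questions. Objective 2 is to "Describe any disparities in the burden of mental health outcomes, including depression and anxiety in people with vitiligo across sociodemographic subgroups". Objective 3 is to "Describe any disparities in the association of vitiligo with parasuicide/suicide attempts, adjustment disorder and sleep disturbances associated with vitiligo across sociodemographic subgroups". Objectives 4 and 5 follow the same pattern for healthcare utilisation and work impact. Section 4.1 adds an aim "to do a subgroup analysis in the vitiligo population to identify health-related disparities across people in different sex, age, deprivation and ethnicity". Section 3.1 gives as part of the rationale that earlier work found "a difference by ethnicity in the mental health impacts of vitiligo" without being designed to assess it.

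On reporting, Section 5 says overall results "will be published, with stratification by age, sex, deprivation and ethnicity". Section 5.7.2 lists the same four factors for stratification, and Section 8.4 refers to an ethnicity subgroup analysis as something already planned.

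On models, the logistic and Cox comparisons in Section 8.3 are all between people with vitiligo and their controls; for objective 3, "Cox proportional hazards regression will be used to estimate the excess risk of parasuicide/suicide attempts in vitiligo cases versus matched controls". The sentence on primary care encounters names a generalised linear model with an offset but no comparator. Section 8.1 says in general terms that baseline characteristics will be related to the outcomes of objectives 2-5 by logistic, Cox and Poisson models. It assigns repeated events to Poisson regression and says assumptions will be checked, with transformations if needed.

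**The concern.** A disparity in the effect of vitiligo is a difference between two stratum effects. It has its own standard error, and neither stratum estimate supplies it. Objective 1 has a stated point of comparison across subgroups (lifetime risk at age 80, Section 8.2); objectives 2-5 have no counterpart. Given only a set of stratum hazard, odds or rate ratios, a reader must judge informally whether they differ. Section 8.1 also sets a p<0.05 threshold, which invites comparison of significant with non-significant strata. A small ethnic group could then appear unaffected, and a large one affected, when the effect is the same in both.

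The target of objective 2 is also not fully fixed. Section 3.2 says "This will include any differences in mental health impact of vitiligo by sociodemographic" and the heading of Section 5.3 is "Disparities in the impact of vitiligo on mental health, healthcare utilisation and work impact". Both point to effect modification against controls, as does the case-control comparison in Section 8.3. The wording of Sections 4.1 and 4.3.1 leaves room for a comparison among people with vitiligo only.

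**Working it through.** **Inputs from the plan.** 8,000 cases, 5% significance level, background prevalence of 15% (anxiety) and 10% (depression), all Section 6; up to four controls per case, Section 7.3.

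**Assumed.** Odds ratio 1.3 in every stratum; strata of 400 and 6,400 cases (5% and 80% of 8,000); full 1:4 matching, with the matching ignored in the variance; two-sided tests and normal approximations. The plan gives no subgroup shares.

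**The plan's own figure.** Section 6 states detectable differences of 1.11% (anxiety) and 1.12% (depression), with versus without vitiligo. The Kelsey formula n = (1.96+0.84)² p̄(1−p̄)(k+1)/(k d²), solved for d at n = 8,000 and k = 4, gives 1.26% and 1.06%, so the stated figures do not reproduce. That is a separate matter and nothing below uses them. What matters here is that the only power statement concerns cases versus controls and says nothing about between-subgroup precision.

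**Step 1: one odds ratio, two strata.** Case risk at control risk 0.10: odds 1.3 × 0.10/0.90 = 0.144, risk 0.126. At 0.15: risk 0.187. SE(log OR) = √(1/a+1/b+1/c+1/d).

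- 400 cases, 1,600 controls, control risk 0.10: √(1/50.5 + 1/349.5 + 1/160 + 1/1,440) = 0.172. Control risk 0.15: 0.146.
- 6,400 cases: a quarter of these, 0.043 and 0.037.
- Power = Φ(ln 1.3/SE − 1.96), with ln 1.3 = 0.262. Small stratum: 0.33 and 0.43. Large stratum: above 0.999 for both.
- Probability that one stratum is significant and the other is not: about 1 − 0.33 = 0.67 and 1 − 0.43 = 0.57. Simulation (200,000 runs) gave 0.65 and 0.56. Hence roughly 56-67%, with no true disparity.

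**Step 2: the contrast that answers the question.** SE of the log ratio of odds ratios = √(0.172² + 0.043²) = 0.177 (control risk 0.10), and 0.151 (0.15).

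- 95% interval factor each way: exp(1.96 × SE) = 1.42 and 1.34.
- Ratio detectable with 80% power: exp(2.80 × SE) = 1.64 and 1.53.
- In the same simulation the interaction test rejected in 5.0% and 4.9% of runs.

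**Step 3: rare outcomes.** Section 9 expects few events for adjustment disorder and parasuicide/suicide. Same split and odds ratio:

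- Assumed control risk 1%: about 5 case events among 400 and 16 control events among 1,600. The SE of the log ratio is 0.524, an interval factor of about 2.8.
- Assumed control risk 0.5%: about 2.6 and 8 events, SE 0.739, factor about 4.3. The normal approximation is itself doubtful here.

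**Step 4: two readings of objective 2.** Take two groups with control risks of 10% and 15% and a common odds ratio of 1.3.

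- Among cases: (1.3 × 0.15/0.85)/(1.3 × 0.10/0.90) = 1.59.
- Against controls: 1.3/1.3 = 1.00.

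The same data show a disparity under one reading and none under the other.

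**Step 5: visit counts.** If variance = φ × mean, a plain Poisson SE is too small by √φ and the true type I error of a 5% test is 2(1 − Φ(1.96/√φ)): 11% at φ = 1.5, 17% at φ = 2, 26% at φ = 3. All values of φ are assumed.

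**The case against.** The strongest defence is that the objectives say only that disparities will be described, that stratified results do describe them, and that Section 8.1 covers the rest by promising models for baseline characteristics and confidence intervals for main effects. Section 3.2 also promises a comparison across sociodemographic groups for healthcare utilisation. This stands in part: it would be wrong to infer that the plan intends no between-subgroup comparison at all. But Section 8.1 names no sociodemographic contrast, and its adjustment sets do not list ethnicity or deprivation. A main effect pooled over cases and controls is also not a difference in the effect of vitiligo. A described disparity still needs an estimate and an interval.

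Second, the 56-67% figure applies only if someone compares significance across strata, and the split of cases is assumed. Both points are correct. The figure shows what can go wrong when no contrast is given; it is not a prediction of what the analysts will do.

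Third, a reader might see a conflict between Poisson regression in Section 8.1 and generalised linear models in Section 8.3. There is none. Poisson regression is a generalised linear model, and an offset with incidence rate ratios fits it. Section 8.3 is only less specific. What remains is that transformations do not repair the variance of overdispersed counts.

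Fourth, interactions are of little use for very rare outcomes. Step 3 bears this out, and the fix is made conditional on event counts.

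**Conclusion.** The point holds in this form: stratified case-control estimates are planned for objectives 2-5, but the contrast between strata, its reference group, its interval and any heterogeneity test are not specified. As written, the analysis section does not define an estimate of the quantity these objectives ask about. It should be corrected before analysis. That conclusion rests on reading Sections 4.3, 8.1 and 8.3 together and on no assumed number. The sizes in the working do depend on the assumed strata, odds ratio and control risks.

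The target of objective 2 needs one clarifying sentence. It is not undefined, since Sections 5.3 and 8.3 favour effect modification against controls. Overdispersion is a minor, separate gap whose size depends on a variance-to-mean ratio that the documents do not give.

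**What to change.** **In Section 8.3, for each endpoint of objectives 2-5 with enough events:**

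- Add vitiligo-by-subgroup interactions for age, sex, ethnicity and deprivation.
- Report one joint heterogeneity test per factor, and ratios of hazard, odds or rate ratios with 95% intervals against a named reference group.
- Base disparity statements on these results, labelled descriptive and without multiplicity control.
- Extend the sufficiency condition of Section 9 to subgroups by stating in advance a minimum event count per subgroup. For parasuicide/suicide attempts and adjustment disorder, give only counts and rates where events fall short.
- State whether objective 2 means effect modification against controls or a comparison within people with vitiligo. If the latter, report the between-group contrast among cases with its interval.

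**For primary care encounters,** use quasi-Poisson or negative binomial regression and keep the time-at-risk offset.

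**Cost.** SAP wording and code; the four factors are already planned stratification variables. Intervals for small subgroups will be wide (Steps 2 and 3), and visit-rate intervals will widen if counts are overdispersed. Some chance findings must be expected. Section 8.3 contains 12 analyses (four for objective 2, three each for objectives 3 and 4, two for objective 5). Four factors give 12 × 4 = 48 joint tests, of which about 48 × 0.05 = 2.4 would fall below 0.05 if no effect differed.
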